- d. All female subjects.
- e. Residential Periods: Discharge from clinic after completion of Day 4 and Day 11 assessments as applicable.
- f. Full physical examination at screening, Day 17 and EDV. Symptom directed examination; if required at any other visits or times at the discretion of the investigator.
- g. Clinical safety laboratory samples (clinical chemistry, haematology and urinalysis) must be performed within 7 days of Day 1; if this interval is exceeded, sampling must be repeated. Samples for clinical chemistry will be obtained following a fast of at least 8 hours (water permitted).
- h. 24 hours post 0-hour dose Day 1 and prior to Day 2, 0-hour dose administration.
- i. Prior to 0-hour dosing.
- j. 24 hours post the 0-hour dose on Day 10.
- k. Performed in triplicate. For assessment of time windows, the time of the first ECG of the triplicate will be used.
- I. Performed at 2 and 4 hours post 0-hour dose.
- m. Pre-dose (0-hour) and post 0-hour dose at 2 and 4 hours.
- n. Systolic and diastolic blood pressure, pulse rate and respiratory rate.
- o. Performed at 0.5, 2, 4, 8 and 12 hours post 0-hour dose. If dosing is BID, the 12-hour assessment will be performed before the evening (i.e. 12-hour) dose.

- p. Pre-dose (0-hour) and post 0-hour dose at 0.5, 2, 4, 8 and 12 hours.
- q. Pre- and post-bronchodilator (salbutamol) reversibility testing at screening. At all other visits and time-points, spirometry may be performed pre- or post-bronchodilator; i.e. there are no requirements for bronchodilator restrictions after the screening visit.
- r. Performed at 0.5, 2, 4 and 8 hours post 0-hour dose.
- s. Pre-dose (0-hour) and post 0-hour dose at 0.5, 2, 4 and 8 hours.
- t. On Days 4 to 9 the subjects will be required to attend the unit for the evening for their 12-hour dose (i.e. return in the evening on Day 4 and attend twice daily on Days 5 to 9) if dosing is BID.
- u. **PK blood samples**: at 1.5, 2, 3, 4 and 12 hours post 0-hour dose. If dosing is BID, the 12-hour sample will be collected before the evening (i.e. 12-hour) dose.
- v. **PK blood sample:** at 24 hours post 0-hour dose Day 1 and prior to Day 2, 0-hour dose administration. If dosing is BID, the 24 hour sample can be taken anytime pre-dose on Day 2.
- w. PK blood samples: Pre-dose (0 hour) and post 0-hour dose at 1.5, 2, 3, 4 and 12 hours.
- x. Induced Sputum Samples for PK assessments: Pre-dose (0 hour) and post 0-hour dose at 3 hours and 6 hours.

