- c. Height and Weight at screening. Weight only on Day 1 (pre-dose) of each treatment period.
- d. All female subjects.
- e. Of the relevant treatment period only, training will be performed pre-dose on Day 1.
- f. Full physical examination at screening Study Day 5 and Study Day 9. Symptom directed examination; if required at any other visits or times at the discretion of the investigator.
- g. Clinical safety laboratory samples (clinical chemistry, haematology and urinalysis) must be performed within 7 days of Day 1, Period 1; if this interval is exceeded, sampling must be repeated. There is no requirement for Day 1 pre-dose laboratory assessment results to be available before dosing in either Period 1 or Period 2. Samples for clinical chemistry will be obtained following a fast of at least 8 hours (water permitted).
- h. Performed in triplicate. For assessment of time windows, the time of the first ECG of the triplicate will be used.
- i. Systolic and diastolic blood pressure, pulse rate and respiratory rate.
- j. Pre and post bronchodilator (salbutamol) reversibility testing at screening. At all other visits and time-points spirometry may be performed pre or post bronchodilator; i.e. there are no requirements for bronchodilator restrictions after the screening visit.
- k. Screening sputum samples will be collected for assessment of eligibility only and will not be analysed.
- A minimum of 6 out of the 16 subjects to be randomised in Part 3 must provide a sufficient sputum sample at screening as per inclusion criteria 13.
- m. Subjects will undergo a SARS-COV-2 RT-PCR test prior to sputum induction at screening. Subjects testing negative may proceed to enrol in the study, provided other eligibility criteria are met; Subjects who test positive should be withdrawn from screening for the study and undergo or be referred for appropriate medical care as determined by local policy for managing a positive result. SARS-COV-2 RT-PCR test must be performed within 14 days of Day 1, Period 1. If this interval is exceeded, sampling must be repeated. Additional RT-PCR testing may be performed throughout the study if deemed necessary by the investigator.
- n. Inhaler device training at screening is to be a demonstration only.

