However, despite promising efficacy in ABPA patients and the improved PK profile, systemic, prolonged use of voriconazole is still associated with a significant number of adverse events and treatment discontinuations, with visual toxicity being one of the main reasons for poor patient tolerability [17]. Development of an inhaled formulation of voriconazole could offer an attractive therapeutic alternative, deprived of the side effects associated with systemic exposure.

ZP-059 (inhaled voriconazole) is an anti-fungal product being developed as a therapeutic for the treatment of ABPA in patients with asthma and cystic fibrosis (CF).

This study will evaluate the safety, tolerability and PK of single and multiple ascending doses of ZP-059 capsules administered as dry powder for inhalation in Part 1 to healthy volunteers (single ascending dose; SAD) and in Part 2 to subjects with mild asthma (multiple ascending dose; MAD), respectively.

In Part 3, the bioavailability of ZP-059 in subjects with mild to moderate stable asthma will be compared to that of oral voriconazole. Part 3 will only start after review of safety data from cohorts 1 to 4 of Part 1 (SAD) have been completed.

Parts 2 and 3 of the study will also explore voriconazole concentrations in induced sputum samples in asthmatic subjects.

As part of the safety and tolerability assessment, this study will investigate the effects of ZP-059 on airway function in both mild and mild to moderate stable asthma subjects.

Population rationale:

ABPA affects both men and women; therefore, a target population of both male and non-pregnant, non-lactating female subjects of childbearing potential (providing they agree to use highly effective contraception) or women of non-childbearing potential between 18 and 60 years will be suitable for all parts of the study (i.e. Parts 1, 2 and 3). As PK of voriconazole has been shown to differ between males and females, in all parts of the study (i.e. Parts 1, 2 and 3) every effort will be made to include as close as possible an equal balance between male and female subjects; in Part 1 and Part 2 this will be in each of the individual cohorts.

Japanese and Chinese subjects will not be included in this study as voriconazole exposures in these populations could be influenced by poor metabolism due to CYP2C19 genotype [18].

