2.3.5. Other

During cannulation, more than one attempt may be needed to insert the cannula in a vein of a subject and it is possible that bruising and/or inflammation may be experienced at the site of cannulation. More rarely fainting, a local clot developing or local infection can occur. At times when a cannula is not required, blood samples will be taken via venepuncture. This can also result in discomfort, bruising or a haematoma at the site of puncture.

Electrocardiogram stickers on the subjects' chests and limbs may cause some local irritation and may be uncomfortable to remove but subjects will be closely monitored to ensure any local irritation does not persist.

Sputum induction is a relatively non-invasive method to obtain sputum for analysis in clinical practice and in research. It is performed using an aerosol of normal and hypertonic saline generated by an ultrasonic nebuliser. Subjects will be pre-treated with a bronchodilator, e.g. 200 to 400 μ g of salbutamol will be administered via a spacer device as required to mitigate against aerosol induced bronchoconstriction. Subjects will be monitored during the procedure (by performing regular lung function), which will be stopped if the subject develops symptoms suggestive of bronchoconstriction or a significant fall (i.e. \geq 20%) in forced expiratory volume in 1 sec (FEV₁), and treated with a bronchodilator as appropriate. Site-specific standard operating procedures (SOPs) for sputum induction will be followed.

All other investigations such as measurements of blood pressure and pulse rate are well established methods which do not present a risk to the subjects.

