6.5.3. Permitted Concomitant Medications for Part 2 (MAD) and Part 3 Crossover)

During Part 2 and Part 3 of the study subjects will be permitted to take the following medications in addition to IMP during the study.

6.5.3.1. Part 2 and Part 3

- Inhaled corticosteroids (ICS) e.g. beclometasone, budesonide, only if the dose is stable from at least 4 weeks prior to screening. On study dosing days, the morning dose should be taken prior to pre-dose spirometry. Evening doses should be taken as logistics allow.
- Short-acting beta-agonists (SABA; e.g. salbutamol, terbutaline). At screening, SABA should be withheld for at least 6 hours prior to pre-bronchodilator spirometry. On study dosing days, SABA should be used as required per subject's symptoms and as required by site-specific SOPs for sputum induction.
- Paracetamol (≤4 g per day).
- Hormonal contraception.
- Hormone replacement therapy (HRT).
- Any medication taken at a stable dose for at least 4 weeks prior to IMP administration that is not specifically prohibited by Section 6.5.4. and is not believed to interfere with the study assessments is acceptable e.g. stable thyroxine, antihypertensives, metformin etc.
- Medication deemed necessary by the investigator to treat AEs.

6.5.3.2. Part 3

- Long-acting beta-agonists (LABA) e.g. formoterol, salmeterol. At screening, LABA should be with-held for at least 12 hours prior to pre-bronchodilator spirometry. On study dosing days, the morning dose should be taken prior to pre-dose spirometry. Evening doses should be taken as logistics allow.
- Ultra-long acting beta-agonist e.g. indacaterol. At screening, ultra-long LABA should be with-held for at least 24 hours prior to pre-bronchodilator spirometry. On study dosing days, the morning dose should be taken prior to pre-dose spirometry. Evening doses should be taken as logistics allow.
- ICS/LABA combination products (e.g. fluticasone + salmeterol, budesonide + formoterol), only if the dose has been stable from at least 4 weeks prior to screening. At screening ICS/LABA should be withheld for at least 12 hours prior to pre-bronchodilator spirometry. On study dosing days, the morning dose should be taken prior to pre-dose spirometry. Evening doses should be taken as logistics allow.

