#### 7.13.4 Pulmonary Function (Spirometry)

Spirometry observed values and change from baseline by parameter will be summarised over time. Parameters will be presented in the same order as the eCRF.

All spirometry data will be listed including change from baseline and reference ranges with flags to indicate all out of range values.

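### Spirometry change from baseline in Parts 2 and 3 ignores bronchodilator timing, so SABA use can mask a fall in FEV1 or create an apparent one

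*Protocol*

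**What the plan says.** Spirometry (FEV1, FVC, PEFR and FEV1/FVC) is part of the primary safety endpoint in all three parts (SAP 3.2.1). Protocol 2.1 adds, as part of the safety and tolerability assessment, that "this study will investigate the effects of ZP-059 on airway function in both mild and mild to moderate stable asthma subjects".

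For Part 2, footnote q of the schedule states that after screening "spirometry may be performed pre- or post-bronchodilator; i.e. there are no requirements for bronchodilator restrictions after the screening visit". For Part 3, footnote j states: "At all other visits and time-points spirometry may be performed pre or post bronchodilator". Day 1 post-dose readings in Part 2 are "Performed at 0.5, 2, 4 and 8 hours post 0-hour dose", and Day 10 uses the same times plus a pre-dose reading.

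Protocol 6.5.3 allows SABA on dosing days for symptoms and "as required by site-specific SOPs for sputum induction". On sputum induction, Protocol 2.3.5 says: "Subjects will be pre-treated with a bronchodilator, e.g. 200 to 400" micrograms of salbutamol. For inhaled corticosteroids in both parts, and for long-acting beta-agonists in Part 3, Protocol 6.5.3 says: "On study dosing days, the morning dose should be taken prior to pre-dose spirometry".

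Baseline is a pre-dose value with no bronchodilator condition (SAP 7.2.1). The planned analysis is: "Spirometry observed values and change from baseline by parameter will be summarised over time" (SAP 7.13.4). Only scheduled post-baseline assessments enter the tables; repeat and unscheduled ones are listed (SAP 7.5.3). Nothing in the SAP flags, splits or sets aside readings by bronchodilator use.

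**The concern.** A change from baseline reflects the study drug only if both readings are taken under comparable bronchodilator conditions. Here they need not be, and the mismatch can depend on the outcome. A subject who bronchoconstricts soon after inhaling ZP-059 may be given salbutamol (Protocol 2.3.3, 8.11.8), and the next scheduled reading is then a treated one. An extra FEV1 taken at symptom onset would be unscheduled, so it would be listed but not tabulated. Conversely, a subject who used SABA shortly before the pre-dose reading has a raised baseline, and its wearing off looks like a fall after dosing.

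Part 2 has no untreated comparator against which to judge either pattern, and its cohorts have 6 subjects, so one or two treated subjects can move a cohort mean visibly. The Part 3 crossover helps with salbutamol given for induction, which is scheduled at the same times in both periods. It does not balance SABA prompted by inhaling ZP-059.

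**Working it through.** The documents give no effect size, SD or power for spirometry, so there is no planned figure to reproduce. The checks below show what could happen and how much of the schedule is exposed.

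**Inputs from the documents.** Cohort size 6 (Part 2) and 16 subjects in two periods (Part 3). The SABA withholding interval before pre-bronchodilator spirometry is 6 h, at screening only (Protocol 6.5.3). A 20% fall in FEV1 is the level at which sputum induction is stopped (Protocol 2.3.5); it is borrowed here as a reference size and is not an expected effect of ZP-059.

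**Assumptions.** SABA raises FEV1 by a proportion g of 5% to 15%. Two of six subjects react and are treated before the reading.

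**1. One subject.**
- SABA after baseline, true fall 20%: recorded fall = 1 - 0.80 × (1 + g).
- SABA before baseline, fully worn off at the reading, no true change: apparent fall = 1 - 1/(1 + g).

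| g | Recorded fall (true 20%) | Apparent fall (true 0%) |
|---|---|---|
| 5% | 16.0% | 4.8% |
| 8% | 13.6% | 7.4% |
| 12% | 10.4% | 10.7% |
| 15% | 8.0% | 13.0% |

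The two mechanisms act in opposite directions and can be of similar size.

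**2. A cohort of six, two treated reactors, four with no change.**
- True mean: -(2 × 20%)/6 = -6.7%.
- As planned, g = 12%: -(2 × 10.4%)/6 = -3.5%. At g = 5% it is -(2 × 16%)/6 = -5.3%; at g = 15% it is -(2 × 8%)/6 = -2.7%.
- With the two treated readings left out: 0/4 = 0%.

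Exclusion is further from the truth than the planned table.

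**3. Exposure of the schedule.**
- Part 2: post-baseline readings per subject are 4 (Day 1) + 1 (Day 2) + 7 (Days 3 to 9) + 5 (Day 10) + 1 + 1 + 1 (Days 11, 14, 17) = 20. Only one, Day 7 pre-dose, shares a time with an induction (1/20 = 5%). The rest depends on symptom-driven SABA, including all of Days 1 and 10.
- Part 3, per period, as read from the broken schedule tables: spirometry at 0.5, 2, 4, 8, 23, 48 and 96 h; induction at 2, 6, 23 and 48 h. The 4 h and 8 h readings follow an induction by 2 h, inside the 6 h interval. The 2, 23 and 48 h readings share a time with an induction, and the protocol does not fix their order. Only 0.5 h and 96 h are clear of induction salbutamol.
- Total: 16 × 2 × 7 = 224 readings. If salbutamol precedes every induction, 16 × 2 × 2 = 64 (29%) are affected. Counting same-time readings, up to 16 × 2 × 5 = 160 (71%) are affected.
- The Period 1 reading at 96 h can also serve as the Period 2 baseline. If it is counted only as that, the denominator is 16 × 13 = 208 and the shares are 31% and 77%.

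**The case against.** The strongest reply is that reactions are captured elsewhere. They are adverse events, and moderate or severe bronchospasm, wheeze and cough are events of special interest (Protocol 8.12.7). FEV1 is monitored frequently in subjects treated for bronchoconstriction (Protocol 8.11.10). Concomitant medication is recorded, summarised and listed (Protocol 6.5.1, SAP 7.9), and all spirometry is listed. Bronchodilator treatment is foreseen for symptomatic bronchoconstriction, so an asymptomatic fall stays visible, and a fall can still show at 0.5 h if no rescue came first.

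This stands as partial cover. It does not close the gap: medication is summarised by class and name with no link to spirometry times, a mild and promptly treated reaction is not an event of special interest, and the special-interest table is produced only if judged necessary.

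Several other points stand in full. The sentence in Protocol 2.1 describes safety monitoring, not a separate airway objective, and no formal analysis of safety data is planned. Taking the morning long-acting beta-agonist before baseline in Part 3 standardises its timing. The eCRF pages, table shells and Study Reference Manual are not available here, so a bronchodilator time field may already exist.

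A reader might also infer that the table drives dose escalation. The documents do not support that: the safety committee reviews spirometry together with adverse events (Protocol 6.6.4), and the SAP says that no outputs will be produced by its authors' organisation for those reviews (SAP 6).

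**Conclusion.** The planned summary can mask or attenuate a fall in FEV1, or produce an apparent one, and as specified it gives no means of telling which. That is a real weakness in one component of the primary safety endpoint and worth correcting at small cost.

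A reader might go further and conclude that the plan hides an airway effect of ZP-059, or biases the mean towards no effect. The documents do not support either. They give no frequency or timing of SABA use, and use before baseline acts in the opposite direction. A reader might also infer that readings after SABA should be dropped from the main table; the cohort example shows why not.

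The figures of -6.7%, -3.5% and 0% rest on an assumed 2-of-6 reaction rate, a 20% fall and a 12% SABA gain. They illustrate the mechanism and do not predict the result. The 29% to 71% exposure in Part 3 assumes salbutamol before every induction. In Part 2 the exposure is almost wholly symptom-driven use, whose extent is unknown.

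**What to change.** Leave every medication rule as it is and change only recording and analysis.

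1. At each Part 2 and Part 3 spirometry reading, record the time and reason (symptoms or sputum induction) of the last SABA, or derive both from the concomitant-medication record if it holds them.
2. In SAP 7.13.4, flag readings and baselines taken within 6 h of a SABA, keeping symptom-driven and induction use separate. The 6 h is the protocol's own screening interval, used here only as an analysis threshold.
3. Keep the all-readings change-from-baseline table as the main summary. Add a sensitivity table without flagged readings, noting that a flagged baseline removes all of that subject's changes from it.
4. For each dose or treatment, tabulate the number of subjects with symptom-driven SABA between dosing and 8 h, and show their lowest post-dose FEV1 before SABA, including unscheduled readings. Restricting the count to symptom-driven use matters in Part 3, where inductions at 2 h and 6 h could otherwise put nearly every subject in it.

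Cost: one or two eCRF fields, SAP wording and extra tables. In Part 3 the sensitivity table may lose about 29% of post-dose readings, and up to 71%, if salbutamol precedes every induction and induction use is also excluded.

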1.2.3. Schedule of Activities for Part 3 (Mild to Moderate Asthmatics)

1.2.3.1 Part 3 Schedule of activities: Screening to Day 4

									T	reat	men	t Per	iod ′	а					
Study Day	-28 to -1	-1						1								2		3	4
Treatment Days								ay 1								Day	2	Day3	Day 4
•										Tir	mes	Afte	r Dos	sing (h	ours)				
Study Procedures	Screen	Adm	Pre- dose														48	72	
Residential Period		•																	─
Informed Consent	Х																		
Medical History (including demographics)	Х																		
Weight and Height c	Х		Х																
Vein Assessment	Х																		
Urine Drug Screen (including Cotinine)	Х	Х																	
Alcohol Breath Test	Х	Х																	
Serum Pregnancy Test ^d	Х																		
Urine Pregnancy Test ^d			Х																
Inhaler Device Training	Xn		Хe																
Randomisation			Х																
IMP Administration				Х															
Physical Examination ^f	Х		Х	•	1		1	ı	1	1	ı	1	1	ı	1	I	→	Х	Х

									Tı	reat	men	t Per	iod 1	а					
Study Day	-28 to -1	-1						1								2		3	4
Treatment Days			Day 1 Times After Dosing (ho													Day	2	Day3	Day 4
•																			
Study Procedures	Screen	Adm	Pre- dose	- 1	0.25	0.5	0.75	1.5	2	3	4	6	8	12	16	23	24	48	72
Residential Period		←																	
Safety Labs ^g	Х		Х													Х			
Serology (HIV/ Hepatitis screen)	Х																		
FSH (postmenopausal females only; if required)	×																		
SARS-CoV-2 Test	×																		
Electrocardiogram	х		Х			Х			Х		Х					Х			
Vital Signs ⁱ	Х		Х			Х			Х		Х		Х	Х		Х		Х	
Tympanic Body Temperature	Х		Х													Х		Х	Χ
Pulse Oximetry	Х		Х			Х			Х		Х		Х	Х		Х		Х	
Spirometry ^j	Х		Х			Х			Х		Х		Х			Х		Х	
Concomitant Medication	4	•	1	1								•	•		1	•		1 1	
Adverse Events	-																		
Blood Samples for PK assessments			Х		Х		Х	Х	Х	Х	Х	Х	Х	Х	Х		Х	Х	
Induced Sputum Samples for PK assessments ^I	Χ¹								х			Х				х		Х	

Part 3 Footnotes

ADM - admission

- a. Washout interval of a minimum of 96 hours between doses in each treatment period i.e. Day 1 dosing to Day 1 of the next treatment period. **Example of minimum washout period**: Period 1, Day 1 Monday the earliest Period 2, Day 1 of the next treatment period is the following Friday.
- b. Screening procedures (including informed consent) can be performed over more than 1 day. Repeat of study procedures is permitted on the day and/or on another day (as appropriate) at the discretion of the investigator.
- c. Height and Weight at screening. Weight only on Day 1 (pre-dose) of each treatment period.
- d. All female subjects.
- e. Of the relevant treatment period only, training will be performed pre-dose on Day 1.
- f. Full physical examination at screening Study Day 5 and Study Day 9. Symptom directed examination; if required at any other visits or times at the discretion of the investigator.
- g. Clinical safety laboratory samples (clinical chemistry, haematology and urinalysis) must be performed within 7 days of Day 1, Period 1; if this interval is exceeded, sampling must be repeated. There is no requirement for Day 1 pre-dose laboratory assessment results to be available before dosing in either Period 1 or Period 2. Samples for clinical chemistry will be obtained following a fast of at least 8 hours (water permitted).
- h. Performed in triplicate. For assessment of time windows, the time of the first ECG of the triplicate will be used.
- i. Systolic and diastolic blood pressure, pulse rate and respiratory rate.
- j. Pre and post bronchodilator (salbutamol) reversibility testing at screening. At all other visits and time-points spirometry may be performed pre or post bronchodilator; i.e. there are no requirements for bronchodilator restrictions after the screening visit.
- k. Screening sputum samples will be collected for assessment of eligibility only and will not be analysed.
- A minimum of 6 out of the 16 subjects to be randomised in Part 3 must provide a sufficient sputum sample at screening as per inclusion criteria 13.
- m. Subjects will undergo a SARS-COV-2 RT-PCR test prior to sputum induction at screening. Subjects testing negative may proceed to enrol in the study, provided other eligibility criteria are met; Subjects who test positive should be withdrawn from screening for the study and undergo or be referred for appropriate medical care as determined by local policy for managing a positive result. SARS-COV-2 RT-PCR test must be performed within 14 days of Day 1, Period 1. If this interval is exceeded, sampling must be repeated. Additional RT-PCR testing may be performed throughout the study if deemed necessary by the investigator.
- n. Inhaler device training at screening is to be a demonstration only.

Permitted windows for all relevant procedures and dosing will be provided in the Study Reference Manual. Where the protocol requires more than one procedure to be completed at the same time point, all efforts will be made to obtain the PK samples at the exact nominal time relative to dosing. Any other procedures scheduled at the same time point will be performed either before or after the PK, as appropriate.

